Adverse reactions to nitazoxanide are related primarily to the gastrointestinal tract with mild and transient abdominal pain (6.6-7.8%), diarrhea (2.1-4.2%), headache (1.1-3.1%), nausea (3.0%) and vomiting (1.1%) being the most common adverse events reported. Mild and transient yellow discoloration of the urine and sclera have also been reported, particularly in patients receiving doses higher than 500 mg bid for extended durations. Other rare adverse events occurring in less than 1% of patients include: asthenia, fever, pain, allergic reaction, pelvic pain, back pain, chills, infection, malaise, flu syndrome, dizziness, somnolence, insomnia, tremor, hyperesthesia, dyspepsia, anorexia, flatulence, constipation, appetite increase, enlarged salivary glands, dry mouth, thirst, dysuria, amenorrhea, metrorrhagia, kidney pain, edema labia, increased creatinine, increased alanine aminotransferase (ALT), anemia, leukocytosis, rash, pruritus, sweating, ear ache, epistaxis, lung disease, pharyngitis, rhinitis, tachycardia, syncope, hypertension, myalgia, leg cramps, and spontaneous bone fracture. No drug-related serious adverse events have been reported during post-marketing experience with nitazoxanide.⁽⁶¹⁻⁷⁰⁾

While nitazoxanide has not shown signs of reproductive toxicity in animal studies, no adequate and well-controlled clinical studies have been conducted in pregnant or lactating females. It is not known whether nitazoxanide is excreted in breast milk. The drug is classified as pregnancy category B by the US FDA. No cases of overdose of nitazoxanide have been reported. Single doses of up to 4000 mg have been reasonably well tolerated in healthy volunteers. There is no specific antidote for nitazoxanide overdose, therefore, management of the patient should consist of symptomatic and supportive therapy.

Antiviral Activity of Nitazoxanide

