abdominal pain within 2-4 days (median 2 days). Clearance of stool virus was variable. Two of 3 patients treated prior to HSCT became negative on stool study within 5-14 days of treatment (1 unknown duration). Among patients treated after HSCT 4 of 9 had persistent viral shedding, 2 received drug until death (1 adenovirus, 1 congestive heart failure) both were treated greater than 2 months, 3 with GVHD continue to shed virus after 6 months of treatment, and 4 have come off therapy and remain negative for Norovirus RNA. One HSCT patient with clinical resolution but persistent viral shedding stopped treatment, resulting in recurrence of clinical symptoms. This patient responded clinically to reinstatement of therapy within 2 days but continued to shed virus. UGI endoscopy/ colonoscopy were performed in 5 pts at the time of infection, all showed inflammation/edema but no GVHD was seen on histology.

Clinical Experience with Nitazoxanide Used for Greater than 3 days

There have been 3 studies (n=505) using nitazoxanide along or in combination with interferon for the treatment of hepatitis C for 3-10 months and one study of prolonged nitazoxanide for patients with AIDS and Cryptosporidiosis who were given 1-1528 days (median 62 days) of nitazoxanide.⁸⁹⁻⁹² In the Cryptosporidiosis study, Fifty-six percent of patients reported a total of 482 adverse events during the course of the study.⁹² Most adverse events (72%) were mild and deemed unrelated to the nitazoxanide. None of the deaths or other serious adverse events (life-threatening or requiring hospitalization) was reported to be related to the use of nitazoxanide. Twenty-seven non-serious adverse events were considered possibly related to the use of the study drug. Twenty of these events were associated with the digestive tract (nausea, vomiting, diarrhea, abdominal pain and dyspepsia). Other events possibly related to treatment were allergic reaction (n = 2), rash (n = 1), yellowish discoloration of the sclera (n = 2), and discoloration of urine (n = 2). Each of these events was transient in nature resolving on treatment or upon the discontinuation of treatment. In the 3 HCV studies, were attributed to the peginterferon and/or the ribavirin without apparent enhancement of the incidence in those patients who received nitazoxanide.⁸⁹⁻⁹¹

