3.2.2 Secondary Outcome Measures

Virologic Efficacy

1. Time from randomization to first negative viral load through 180 days.
2. The change in viral titer between Day 1 and 180.

Safety

3. Incidence of unsolicited non-serious adverse events (see section 9 for details) through 60 days.
4. Incidence of laboratory adverse events (WBC, Hemoglobin, Platelet Count, Creatinine, Alkaline Phosphatase, ALT, AST, BUN and Bilirubin) through 60 days.
5. Incidence of protocol-specified serious adverse events (see section 9 for details) through 60 days.
6. Incidence of Hospitalization through 60 days.

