9.2 Methods and Timing for Assessing, Recording, and Analyzing Safety Parameters

9.2.1 Adverse Events

ICH E6 defines an AE as any untoward medical occurrence in a patient or clinical investigation subject administered a pharmaceutical product regardless of its causal relationship to the study treatment. FDA defines an AE as any untoward medical occurrence associated with the use of a drug in humans, whether or not considered drug related.

An AE can therefore be any unfavorable and unintended sign (including an abnormal laboratory finding), symptom, or disease temporally associated with the use of medicinal (investigational) product. The occurrence of an AE may come to the attention of study personnel during study visits and interviews of a study recipient presenting for medical care, or upon review by a study monitor

Unsolicited clinical AEs are those non serious AEs that are **not** being collected as clinical outcome measures. For this study, unsolicited clinical AEs to be captured on the appropriate case report form, will be only those clinical AEs that meet either of the following criteria through 60 days:

- Result in modification in the administration of the study drug (nitazoxanide or placebo).
- Result in discontinuation of the study drug (nitazoxanide or placebo).

The following solicited safety laboratory parameters will be assessed on Day 7, 28 and 60: WBC, Hemoglobin, Platelet count, Creatinine, Alkaline Phosphatase, ALT, AST, BUN and Bilirubin. Additional laboratory parameters performed as part of the CBC and complete metabolic panel results need to be recorded in the source document with the evaluation of the site physician. Those additional laboratory value will need to be reported as AE only if clinically significant and not attributable to Norovirus infection or underlying SOT/HSCT medical conditions.

Abnormal values observed in the clinical laboratory assessment that are conducted by the clinical team outside the study visits, will be reported as AE only if the site physician assess that the laboratory value is clinically significant and not attributable to Norovirus infection or underlying SOT/HSCT medical conditions. The evaluation should be recorded in the source documents.

Laboratory AEs will be reported as defined in section 9.2.3.

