9.5 Halting Rules

Further enrollment will be halted for DSMB review/recommendation if any of the following are reported through Day 60:

- Two or more subjects experience a study product-related SAE.
- ≥ 4 subjects experience the same severe (Grade 3) study product-related unsolicited AE until 80 subjects enrolled or $\geq 5\%$ or more subjects experience the same severe (Grade 3) study product-related unsolicited AE after 80 subjects have been enrolled.
- ≥ 4 subjects experience the same severe (Grade 3) study product-related safety laboratory AE until 80 subjects enrolled or $\geq 5\%$ or more subjects experience the same severe (Grade 3) study product-related safety laboratory AE after 80 subjects have been enrolled.

Further enrollment will be halted for DSMB review/recommendation if the ratio of each clinical adverse outcome incidence rate per subject between the study arms is two or higher through Day 180:

- Death: Minimum of 4 or more subjects experience death in all study arms.
- Hospitalization: Minimum of 10 or more subjects experience hospitalization in all study arms.
- Graft rejection: Minimum of 5 or more subjects experience graft rejection in all study arms.
- Graft loss: Minimum of 5 or more subjects experience graft loss in all study arms
- Renal insufficiency, defined as a 20% or greater increase in serum creatinine relative to screening/enrollment/baseline value: Minimum of 10 or more subjects experience renal insufficiency in all study arms.

DMID retains the authority to suspend additional enrollment and study interventions/administration of study product during the entire study, as applicable.

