4.5.3. Safety Variables

The safety of nitazoxanide will be assessed by the frequency of protocol specified unsolicited clinical adverse events, laboratory adverse events and serious adverse events.

Unsolicited Adverse Events (AEs):

Unsolicited clinical Adverse Events are those non serious AEs that are not being collected as clinical outcome measures. For this study, unsolicited clinical AEs to be captured on the appropriate case report form, will be only those clinical AEs that meet either of the following criteria through 60 days:

- Result in modification in the administration of the study drug (nitazoxanide or placebo).
- Result in discontinuation of the study drug (nitazoxanide or placebo).

Any medical condition that is present at the time that the subject is screened should be considered as baseline and not reported as an AE. However, if it deteriorates at any time during the study, it should be recorded as an AE as defined above.

Unsolicited clinical AEs will be assigned the severity level of Grade 3.

The clinician's assessment of an AE's relationship to test article (study drug) is part of the documentation process, but it is not a factor in determining what is or is not reported in the study. If there is any doubt as to whether a clinical observation is an AE, the event should be reported. AEs must have their relationship to study product assessed using the terms: related or not related. In a clinical trial, the study product must always be suspect. To help assess, the following guidelines are used.

- Related – There is a reasonable possibility that the study product caused the adverse event. Reasonable possibility means that there is evidence to suggest a causal relationship between the study product and the adverse event.
- Not Related – There is not a reasonable possibility that the administration of the study product caused the event.

Safety Laboratory Parameters:

The following solicited safety laboratory parameters will be assessed on Day 7, 28 and 60: WBC, Hemoglobin, Platelet count, Creatinine, Alkaline Phosphatase, ALT, AST, BUN and Bilirubin. Additional laboratory parameters performed as part of the CBC and complete metabolic panel results need to be recorded in the source document with the evaluation of the site physician. Those additional laboratory values will need to be reported as AEs only if clinically significant and not attributable to Norovirus infection or underlying SOT/HSCT medical conditions.

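### Non-serious diarrhea or vomiting that makes a subject stop study drug is not an adverse event under the plan's definition, so the main safety table can miss the kind of intolerance expected of nitazoxanide

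*Protocol*

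**What the plan says.** **Expected toxicity.** Protocol 2.1 states: "Adverse reactions to nitazoxanide are related primarily to the gastrointestinal tract with mild and transient abdominal pain (6.6-7.8%), diarrhea (2.1-4.2" percent), and continues after headache with "nausea (3.0%) and vomiting (1.1%) being the most common adverse events reported". On prolonged dosing, it reports 27 non-serious events considered possibly related in the AIDS cryptosporidiosis study: "Twenty of these events were associated with the digestive tract (nausea, vomiting, diarrhea, abdominal pain and dyspepsia").

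**Definition.** Protocol 9.2.1: "Unsolicited clinical AEs are those non serious AEs that are not being collected as clinical outcome measures". SAP 4.5.3 repeats it: "Unsolicited clinical Adverse Events are those non serious AEs that are not being collected as clinical outcome measures". Both then capture, within that set, only events through Day 60 that modify or stop study drug. Both say that a baseline condition which deteriorates is recorded as an adverse event, but under the definition just given.

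**Where the category is used.** It is a secondary safety outcome in Protocol 3.2.2: "Incidence of unsolicited non-serious adverse events (see section 9 for details) through 60 days". SAP 9.3 reports it by arm in Table 50, with a difference, a 95% confidence interval and Barnard's test. It also feeds a count in Protocol 9.5, where enrollment is halted if enough subjects "experience the same severe (Grade 3) study product-related unsolicited AE".

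**What is collected as an outcome.** Diarrhea (Bristol type 6 or 7) and vomiting make up the primary endpoint (Protocol 3.2.1). Nausea and belly pain are domains of the PROMIS GI questionnaire (SAP 3.3), which is exploratory outcome 13 in Protocol 3.2.3.

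**The concern.** The order of the two conditions matters. A symptom that is an outcome leaves the category before anyone asks whether it stopped treatment, so the discontinuation criterion cannot bring it back. The symptoms removed include ones that the protocol lists among the drug's most common reactions.

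Safety is a secondary objective, and Table 50 is the planned between-arm answer. If more nitazoxanide than placebo subjects stop tablets because of non-serious diarrhea or vomiting, its unsolicited-event row does not move. A reader of the study report could take that row as evidence of good tolerability when the definition has ruled out the relevant finding.

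**Working it through.** The plan gives no figure on this point to reproduce. The check sets the texts side by side and then sizes what is left out.

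**Step 1. Which symptoms are excluded?** Expected counts are rate × n, at the Protocol 2.1 rates. n = 80 is the planned arm. n = 15 is an assumption from 31 enrolled (SAP 6.6) at 1:1.

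| Symptom | Rate | Collected as | Excluded? | Of 80 | Of 15 |
|---|---|---|---|---|---|
| Diarrhea | 2.1–4.2% | Primary endpoint | Yes | 1.7–3.4 | 0.3–0.6 |
| Vomiting | 1.1% | Primary endpoint | Yes | 0.9 | 0.2 |
| Nausea | 3.0% | Exploratory PROMIS GI | Probably; not stated | 2.4 | 0.45 |
| Abdominal pain | 6.6–7.8% | Exploratory PROMIS GI | Probably; not stated | 5.3–6.2 | 1.0–1.2 |

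These rates cover all severities. Only events that modify or stop drug could be captured under any reading, and the documents give no rate for those. The counts are therefore illustrations, not estimates of missed events.

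**Step 2. What share of the listed reactions is clearly excluded?** With headache at 1.1–3.1%, the stated frequencies sum to 6.6 + 2.1 + 1.1 + 3.0 + 1.1 = 13.9% at the low end and 7.8 + 4.2 + 3.1 + 3.0 + 1.1 = 19.2% at the high end.

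- Diarrhea plus vomiting, low end: (2.1 + 1.1)/13.9 = 3.2/13.9 = 23%.
- Diarrhea plus vomiting, high end: (4.2 + 1.1)/19.2 = 5.3/19.2 = 28%.

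For prolonged dosing, 20/27 = 74% of the possibly related non-serious events were digestive. That is an upper bound on the excluded share, because the 20 include dyspepsia, which is not an outcome here.

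**Step 3. Does another planned analysis catch a subject who stops drug for diarrhea or vomiting?**

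- *Time to withdrawal for intolerance* (SAP 4.5.4 and 11, Table 108): partly. It is exploratory and built only on subjects who terminated early. Protocol 5.3.4 treats stopping the intervention as distinct from leaving the study and asks subjects who withdraw after dosing to continue study procedures. A subject who stops tablets and stays in follow-up is missed.
- *Table 49, adverse events leading to early termination*: no. Its footnote takes these from the adverse-event form, so it inherits the exclusion.
- *Efficacy comparisons*: partly. Table 30 compares diarrhea days and stool counts, and Table 33 compares PROMIS nausea and belly pain. Neither links a symptom to stopping drug.
- *Diary complaints*: no. Protocol 9.1 names them as a safety parameter, but SAP section 9 plans no safety analysis of diary symptoms.
- *Listing 2*: it holds the reasons for treatment discontinuation, but as a subject-level listing without a comparison by arm.

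**The case against.** The strongest case against has four parts.

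**Attribution is hard here.** Every subject must have had recent active diarrhea to enter, so comparing symptoms by randomized arm is defensible. This stands as a reason not to attribute every symptom. It does not explain why stopping drug for a symptom should go uncounted.

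**Intolerance is already reviewed.** SAP 4.5.4 plans a blinded review of termination reasons and analyzes them by arm. This stands in part, and it narrows the gap to subjects who stop or interrupt drug without leaving the study, plus the absence of any such count from the main safety table.

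**Sites are told to report when in doubt.** Both documents include that instruction. It pulls against the explicit exclusion without overriding it, so sites may have recorded such events differently. That is itself a reason to reconcile the texts.

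**The exclusion does not reach everything.** This stands. A reader might infer that no gastrointestinal reaction can ever be an adverse event, or that 84–92% of the listed reaction frequency is lost (16.1/19.2 and 12.8/13.9, counting all four symptoms). The documents do not support that:

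- Serious gastrointestinal events remain SAEs, and admissions have their own row in Table 50.
- Terms that are not outcomes, such as dyspepsia and constipation, can still be captured.
- The status of nausea and abdominal pain turns on whether a PROMIS score counts as a clinical outcome measure, which is never stated. SAP 4.5.4 keeps graft rejection and loss, also exploratory outcomes, off the unsolicited-event form, but by an explicit instruction and with a dedicated form. No such instruction names gastrointestinal symptoms.
- Protocol 2.3.1 lists abdominal pain, headache, chromaturia and nausea as most common. Vomiting is absent there, and diarrhea appears only among post-approval reports.

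**Conclusion.** The point holds on the literal text for diarrhea and vomiting. Non-serious episodes that lead a subject to stop study drug contribute zero to the unsolicited-event row of Table 50, whatever their true number. For nausea and abdominal pain the exclusion is a plausible reading, not an established one.

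The number of subjects affected cannot be derived from the documents. With 31 enrolled it is likely to be small, and the clearly excluded symptoms make up 23–28% of the listed reaction frequency. The harm is to interpretation: a low count in that row would not be evidence of gastrointestinal tolerability.

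A reader might also infer that a live stopping safeguard is disabled. The unsolicited-event count in Protocol 9.5 does share the definition, but enrollment has ended, so this is now only a matter of record.

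The conclusion assumes that sites followed the written definition. If they reported such events under the in-doubt instruction, Table 50 would mix two conventions, and clarification would still be needed.

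**What to change.** 1. **Reconcile the definition.** State, for Protocol 9.2.1 and SAP 4.5.3 together, whether a gastrointestinal symptom recorded as the reason for modifying or stopping study drug is an adverse event when it is also an outcome. Say whether PROMIS GI domains count as clinical outcome measures, and how the in-doubt and worsening sentences fit.
2. **Extend the blinded review.** Apply the review of termination reasons in SAP 4.5.4 to all treatment discontinuations in Listing 2, including those of subjects who stayed in follow-up.
3. **Add one descriptive row by arm to Table 50**: gastrointestinal symptom leading to study drug discontinuation. Keep it separate from the adverse-event rows. Both documents assign Grade 3 to every unsolicited clinical adverse event, and merging would label these symptoms severe automatically.

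**Cost.** A short clarification, a blinded reading of reasons already held for 31 subjects, and one table row. No dosing rule or halting threshold changes.

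**Limits.** Some disease-related symptoms will be counted in both arms; placebo shows that background. The review depends on the recorded reasons being specific enough to identify a gastrointestinal symptom. Interruptions without a recorded reason cannot be recovered, since Listing 8 shows missed doses but not why they were missed.

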abdominal pain within 2-4 days (median 2 days). Clearance of stool virus was variable. Two of 3 patients treated prior to HSCT became negative on stool study within 5-14 days of treatment (1 unknown duration). Among patients treated after HSCT 4 of 9 had persistent viral shedding, 2 received drug until death (1 adenovirus, 1 congestive heart failure) both were treated greater than 2 months, 3 with GVHD continue to shed virus after 6 months of treatment, and 4 have come off therapy and remain negative for Norovirus RNA. One HSCT patient with clinical resolution but persistent viral shedding stopped treatment, resulting in recurrence of clinical symptoms. This patient responded clinically to reinstatement of therapy within 2 days but continued to shed virus. UGI endoscopy/ colonoscopy were performed in 5 pts at the time of infection, all showed inflammation/edema but no GVHD was seen on histology.

Clinical Experience with Nitazoxanide Used for Greater than 3 days

There have been 3 studies (n=505) using nitazoxanide along or in combination with interferon for the treatment of hepatitis C for 3-10 months and one study of prolonged nitazoxanide for patients with AIDS and Cryptosporidiosis who were given 1-1528 days (median 62 days) of nitazoxanide.⁸⁹⁻⁹² In the Cryptosporidiosis study, Fifty-six percent of patients reported a total of 482 adverse events during the course of the study.⁹² Most adverse events (72%) were mild and deemed unrelated to the nitazoxanide. None of the deaths or other serious adverse events (life-threatening or requiring hospitalization) was reported to be related to the use of nitazoxanide. Twenty-seven non-serious adverse events were considered possibly related to the use of the study drug. Twenty of these events were associated with the digestive tract (nausea, vomiting, diarrhea, abdominal pain and dyspepsia). Other events possibly related to treatment were allergic reaction (n = 2), rash (n = 1), yellowish discoloration of the sclera (n = 2), and discoloration of urine (n = 2). Each of these events was transient in nature resolving on treatment or upon the discontinuation of treatment. In the 3 HCV studies, were attributed to the peginterferon and/or the ribavirin without apparent enhancement of the incidence in those patients who received nitazoxanide.⁸⁹⁻⁹¹

Twenty-seven non-serious adverse events were considered possibly related to the use of the study drug. Twenty of these events were associated with the digestive tract (nausea, vomiting, diarrhea, abdominal pain and dyspepsia). Other events possibly related to treatment were allergic reaction (n = 2), rash (n = 1), yellowish discoloration of the sclera (n = 2), and discoloration of urine (n = 2). Each of these events was transient in nature resolving on treatment or upon the discontinuation of treatment. In the 3 HCV studies, were attributed to the peginterferon and/or the ribavirin without apparent enhancement of the incidence in those patients who received nitazoxanide.⁸⁹⁻⁹¹

